### **D. Genomic Research**

Genomic research will only be conducted in accordance with a protocol and informed consent authorized by an ethics committee.

## **IV. Financial Considerations**

### **A. Payments to Investigators**

Clinical trials are time- and labor-intensive. It is MSD's policy to compensate investigators (or the sponsoring institution) in a fair manner for the work performed in support of MSD trials. MSD does not pay incentives to enroll participants in its trials. However, when enrollment is particularly challenging, additional payments may be made to compensate for the time spent in extra recruiting efforts.

MSD does not pay for participant referrals. However, MSD may compensate referring physicians for time spent on chart review to identify potentially eligible participants.

**B. Clinical Research Funding**

Informed consent forms will disclose that the trial is sponsored by MSD and that the investigator or sponsoring institution is being paid or provided a grant for performing the trial. However, the local ethics committee may wish to alter the wording of the disclosure statement to be consistent with financial practices at that institution. As noted above, all publications resulting from MSD trials will indicate MSD as a source of funding.

**C. Funding for Travel and Other Requests**

Funding of travel by investigators and support staff (eg, to scientific meetings, investigator meetings, etc.) will be consistent with local guidelines and practices.

**V. Investigator Commitment**

Investigators will be expected to review MSD's Code of Conduct as an appendix to the trial protocol, and in signing the protocol, agree to support these ethical and scientific standards.

**10.1.2 Financial Disclosure**

Financial Disclosure requirements are outlined in the US Food and Drug Administration Regulations, Financial Disclosure by Clinical Investigators (21 CFR Part 54). It is the Sponsor's responsibility to determine, based on these regulations, whether a request for Financial Disclosure information is required. It is the investigator's/subinvestigator's responsibility to comply with any such request.

The investigator/subinvestigator(s) agree, if requested by the Sponsor in accordance with 21 CFR Part 54, to provide his/her financial interests in and/or arrangements with the Sponsor to allow for the submission of complete and accurate certification and disclosure statements.

The investigator/subinvestigator(s) further agree to provide this information on a Certification/Disclosure Form, commonly known as a financial disclosure form, provided by the Sponsor. The investigator/subinvestigator(s) also consent to the transmission of this information to the Sponsor in the United States for these purposes. This may involve the transmission of information to countries that do not have laws protecting personal data.

**10.1.3 Data Protection**

Participants will be assigned a unique identifier by the Sponsor. Any participant records or datasets that are transferred to the Sponsor will contain the identifier only; participant names or any information that would make the participant identifiable will not be transferred.

The participant must be informed that his/her personal study-related data will be used by the Sponsor in accordance with local data protection law. The level of disclosure must also be explained to the participant.

The participant must be informed that his/her medical records may be examined by Clinical Quality Assurance auditors or other authorized personnel appointed by the Sponsor, by appropriate IRB/IEC members, and by inspectors from regulatory authorities.

### **10.1.3.1 Confidentiality of Data**

By signing this protocol, the investigator affirms to the Sponsor that information furnished to the investigator by the Sponsor will be maintained in confidence, and such information will be divulged to the IRB, IEC, or similar or expert committee; affiliated institution and employees, only under an appropriate understanding of confidentiality with such board or committee, affiliated institution and employees. Data generated by this study will be considered confidential by the investigator, except to the extent that it is included in a publication as provided in the Publications section of this protocol.

### **10.1.3.2 Confidentiality of Participant Records**

By signing this protocol, the investigator agrees that the Sponsor (or Sponsor representative), IRB/IEC, or regulatory authority representatives may consult and/or copy study documents to verify worksheet/CRF data. By signing the consent form, the participant agrees to this process. If study documents will be photocopied during the process of verifying worksheet/CRF information, the participant will be identified by unique code only; full names/initials will be masked prior to transmission to the Sponsor.

By signing this protocol, the investigator agrees to treat all participant data used and disclosed in connection with this study in accordance with all applicable privacy laws, rules and regulations.

### **10.1.3.3 Confidentiality of IRB/IEC Information**

The Sponsor is required to record the name and address of each IRB/IEC that reviews and approves this study. The Sponsor is also required to document that each IRB/IEC meets regulatory and ICH GCP requirements by requesting and maintaining records of the names and qualifications of the IRB/IEC members and to make these records available for regulatory agency review upon request by those agencies.

### **10.1.4 Committees Structure**

Not applicable for this study.

### **10.1.5 Publication Policy**

The results of this study may be published or presented at scientific meetings. The Sponsor will comply with the requirements for publication of study results. In accordance with standard editorial and ethical practice, the Sponsor will generally support publication of multicenter studies only in their entirety and not as individual site data. In this case, a coordinating investigator will be designated by mutual agreement.

If publication activity is not directed by the Sponsor, the investigator agrees to submit all manuscripts or abstracts to the Sponsor before submission. This allows the Sponsor to protect proprietary information and to provide comments.

Authorship will be determined by mutual agreement and in line with International Committee of Medical Journal Editors authorship requirements.

#### **10.1.6 Compliance with Study Registration and Results Posting Requirements**

Under the terms of the Food and Drug Administration Amendments Act (FDAAA) of 2007 and the European Medicines Agency (EMA) clinical trial Directive 2001/20/EC, the Sponsor of the study is solely responsible for determining whether the study and its results are subject to the requirements for submission to <http://www.clinicaltrials.gov>, [www.clinicaltrialsregister.eu](http://www.clinicaltrialsregister.eu) or other local registries. MSD, as Sponsor of this study, will review this protocol and submit the information necessary to fulfill these requirements. MSD entries are not limited to FDAAA or the EMA clinical trial directive mandated trials. Information posted will allow participants to identify potentially appropriate studies for their disease conditions and pursue participation by calling a central contact number for further information on appropriate study locations and study site contact information.

By signing this protocol, the investigator acknowledges that the statutory obligations under FDAAA, the EMA clinical trials directive, or other locally mandated registries are that of the Sponsor and agrees not to submit any information about this study or its results to those registries.

#### **10.1.7 Compliance with Law, Audit, and Debarment**

By signing this protocol, the investigator agrees to conduct the study in an efficient and diligent manner and in conformance with this protocol; generally accepted standards of GCP (eg, International Conference on Harmonization of Technical Requirements for Registration of Pharmaceuticals for Human Use GCP: Consolidated Guideline and other generally accepted standards of GCP); and all applicable federal, state and local laws, rules and regulations relating to the conduct of the clinical study.

The Code of Conduct, a collection of goals and considerations that govern the ethical and scientific conduct of clinical investigations sponsored by MSD, is provided in this appendix under the Code of Conduct for Clinical Studies.

The investigator agrees not to seek reimbursement from participants, their insurance providers, or from government programs for procedures included as part of the study reimbursed to the investigator by the Sponsor.

The investigator will promptly inform the Sponsor of any regulatory authority inspection conducted for this study.

The investigator agrees to provide the Sponsor with relevant information from inspection observations/findings to allow the Sponsor to assist in responding to any citations resulting from regulatory authority inspection and will provide the Sponsor with a copy of the proposed response for consultation before submission to the regulatory authority.

Persons debarred from conducting or working on clinical studies by any court or regulatory authority will not be allowed to conduct or work on this Sponsor's studies. The investigator will immediately disclose in writing to the Sponsor if any person who is involved in conducting the study is debarred or if any proceeding for debarment is pending or, to the best of the investigator's knowledge, threatened.

#### **10.1.8 Data Quality Assurance**

All participant data relating to the study will be recorded on printed or electronic CRF unless transmitted to the Sponsor or designee electronically (eg, laboratory data). The investigator or qualified designee is responsible for verifying that data entries are accurate and correct by physically or electronically signing the CRF.

Detailed information regarding Data Management procedures for this protocol will be provided separately.

The investigator must maintain accurate documentation (source data) that supports the information entered in the CRF.

The investigator must permit study-related monitoring, audits, IRB/IEC review, and regulatory agency inspections and provide direct access to source data documents.

Study documentation will be promptly and fully disclosed to the Sponsor by the investigator upon request and also shall be made available at the study site upon request for inspection, copying, review, and audit at reasonable times by representatives of the Sponsor or any regulatory authorities. The investigator agrees to promptly take any reasonable steps that are requested by the Sponsor or any regulatory authorities as a result of an audit or inspection to cure deficiencies in the study documentation and worksheets/CRFs.

The Sponsor or designee is responsible for the data management of this study including quality checking of the data.

Study monitors will perform ongoing source data review and verification to confirm that data entered into the CRF by authorized site personnel are accurate, complete, and verifiable from source documents; that the safety and rights of participants are being protected; and that the study is being conducted in accordance with the currently approved protocol and any other study agreements, ICH GCP, and all applicable regulatory requirements.

Records and documents, including signed ICF, pertaining to the conduct of this study must be retained by the investigator for 15 years after study completion unless local regulations or institutional policies require a longer retention period. No records may be destroyed during the retention period without the written approval of the Sponsor. No records may be transferred to another location or party without written notification to the Sponsor.

### **10.1.9 Source Documents**

Source documents provide evidence for the existence of the participant and substantiate the integrity of the data collected. The investigator/institution should maintain adequate and accurate source documents and study records that include all pertinent observations on each of the site's participants. Source documents and data should be attributable, legible, contemporaneous, original, accurate, and complete. Changes to source data should be traceable, should not obscure the original entry, and should be explained if necessary (eg, via an audit trail). Source documents are filed at the investigator's site.

Data reported on the CRF or entered in the eCRF that are transcribed from source documents must be consistent with the source documents or the discrepancies must be explained. The investigator/institution may need to request previous medical records or transfer records, depending on the study. Also, current medical records must be available.

### **10.1.10 Study and Site Closure**

The Sponsor or its designee may stop the study or study site participation in the study for medical, safety, regulatory, administrative, or other reasons consistent with applicable laws, regulations, and GCP.

In the event the Sponsor prematurely terminates a particular study site, the Sponsor will promptly notify that study site's IRB/IEC.

## 10.2 Appendix 2: Clinical Laboratory Tests

- The tests with marker of \* listed in **Table 9** will be performed by the local laboratory at Visit 1.
- Protocol-specific requirements for inclusion or exclusion of participants are detailed in Section 5 of the protocol.
- Additional tests may be performed at any time during the study as determined necessary by the investigator or required by local regulations.

Table 9 Protocol-required Laboratory Assessments

Laboratory Assessments	Parameters					
Hematology*	Platelet Count	RBC Indices: MCV MCH %Reticulocytes		WBC count with Differential: Neutrophils Lymphocytes Monocytes Eosinophils Basophils		
	RBC Count					
	Hemoglobin					
	Hematocrit					
Chemistry*	Blood Urea Nitrogen (BUN)	Potassium	Aspartate Aminotransferase (AST)/ Serum Glutamic-Oxaloacetic Transaminase (SGOT)	Total bilirubin (and direct bilirubin, if total bilirubin is elevated above the upper limit of normal)		
	Albumin	CK (CPK)	Chloride	eGFR		
	Creatinine	Sodium Calcium Potassium Phosphorous Bicarbonate	Alanine Aminotransferase (ALT)/ Serum Glutamic-Pyruvic Transaminase (SGPT)	Total Protein		
	Glucose (fasting)	Uric acid	Alkaline phosphatase (ALP)	$\gamma$ -glutamyl transferase		
Lipid Panel A*	LDL-C	HDL-C non-HDL-C	total cholesterol (TC)	Triglyceride (TG)		
Routine Urinalysis*	Specific gravity	pH, glucose, protein, blood, ketones, [bilirubin, urobilinogen, nitrite, leukocyte esterase] by dipstick		Microscopic examination (if blood or protein is abnormal)		
Apolipoprotein Evaluations	
 
Apolipoprotein B (Apo B)
 
					
Pregnancy test	
 
Urine pregnancy test (urine hCG) will be determined at the site (as needed for WOCBP).
 
Serum <math>\beta</math>-hCG test will be required if urine pregnancy result is positive.
 
					
Other Laboratory Tests	
 
Follicle-stimulating hormone (FSH): only applicable for perimenopausal women.
 
Thyroid stimulating hormone (TSH), fT4
 
					

Laboratory Assessments	Parameters
NOTES:	
* Laboratory tests results received within 4 weeks prior to screening visit is acceptable as screening test to check the eligibility.	

The investigator (or medically qualified designee) must document their review of each laboratory safety report.

All lipid evaluations results will be blinded to participants and to study team once the participant is centrally randomized. No attempts could be made to have local evaluation of the participant's lipid levels once they have successfully entered the double blind treatment phase. The investigator will not be blinded to laboratory safety results. Emergency treatment code breaks should only be undertaken when it is essential to treat the participant safely and efficaciously. Most often, study drug discontinuation and knowledge of the possible treatment assignments are sufficient to treat a study participant who presents with an emergency condition. In case that emergency unblinding is required, investigator should start the process after consultation and discussion with sponsor.

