### **6.8      Clinical Supplies Disclosure**

The emergency unblinding call center will use the intervention/randomization schedule for the study to unblind participants and to unmask study intervention identity. The emergency unblinding call center should only be used in cases of emergency (see Section 8.1.11). In the event that the emergency unblinding call center is not available for a given site in this study, the central electronic intervention allocation/randomization system (IRT) should be used to unblind participants and to unmask study intervention identity. The Sponsor will not provide random code/disclosure envelopes or lists with the clinical supplies.

Each study site will be supplied by Sponsor with the investigational treatment.

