### **8.1.3 Participant Identification Card**

All participants will be given a participant identification card identifying them as participants in a research study. The card will contain study site contact information (including direct telephone numbers) to be used in the event of an emergency. The investigator or qualified designee will provide the participant with a participant identification card immediately after

the participant provides written informed consent. At the time of intervention allocation/randomization, site personnel will add the treatment/randomization number to the participant identification card.

The participant identification card also contains contact information for the emergency unblinding call center so that a healthcare provider can obtain information about study intervention in emergency situations where the investigator is not available.

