### 8.1.11 Participant Blinding/Unblinding

STUDY INTERVENTION IDENTIFICATION INFORMATION IS TO BE UNMASKED ONLY IF NECESSARY FOR THE WELFARE OF THE PARTICIPANT. EVERY EFFORT SHOULD BE MADE NOT TO UNBLIND.

For emergency situations where the investigator or medically qualified designee (consistent with local requirements) needs to identify the intervention used by a participant and/or the dosage administered, he/she will contact the emergency unblinding call center by telephone and make a request for emergency unblinding. As requested by the investigator or medically qualified designee, the emergency unblinding call center will provide the information to him/her promptly and report unblinding to the Sponsor. Prior to contacting the emergency unblinding call center to request unblinding of a participant's intervention assignment, the investigator who is a qualified physician should make reasonable attempts to enter the intensity of the AEs observed, the relation to study intervention, the reason thereof, etc., in the medical chart. If it is not possible to record this assessment in the chart prior to the unblinding, the unblinding should not be delayed.

In the event that unblinding has occurred, the circumstances around the unblinding (eg, date, reason, and person performing the unblinding) must be documented promptly, and the Sponsor Clinical Director notified as soon as possible. Once an emergency unblinding that is part of the study design has taken place, the principal investigator, site personnel, and Sponsor personnel may be unblinded so that the appropriate follow-up medical care can be provided to the participant.

Participants will remain blind to the identity of the treatment from Visit 4 until database lock, using the following methods:

- Randomization data are kept strictly confidential until the time of unblinding, and will not be accessible by anyone involved in the study;
- The identity of the treatment will be concealed by using the identical packaging, labeling, appearance, taste and color. And a double-dummy design is used because differences between investigational treatment and comparator cannot be disguised due to their different appearance;
- Lipid panel test after randomization will be done centrally and the result will not reveal to the participants or study team until end of the study. No attempts could be made to have local evaluation of the lipid levels once the participant successfully entered the double blind treatment phase.

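### Appendix 2 puts sponsor consultation ahead of a required emergency unblinding, a step that the unblinding procedure itself does not contain and that could delay a needed code break

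*Combined protocol and SAP*

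**What the plan says.** Emergency unblinding is covered in four places.

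- **Section 10.2 (Appendix 2, Clinical Laboratory Tests).** It first sets a threshold: "Emergency treatment code breaks should only be undertaken when it is essential to treat the participant safely and efficaciously". It adds that stopping the drug and knowing the possible assignments are usually enough. It then closes with: "In case that emergency unblinding is required, investigator should start the process after consultation and discussion with sponsor".
- **Section 8.1.11 (Participant Blinding/Unblinding).** When the investigator or a medically qualified designee needs the assignment in an emergency, "he/she will contact the emergency unblinding call center by telephone and make a request for emergency unblinding". On that request, "the emergency unblinding call center will provide the information to him/her promptly and report unblinding to the Sponsor". Once unblinding has taken place, the circumstances "must be documented promptly, and the Sponsor Clinical Director notified as soon as possible".
- **Section 6.8 (Clinical Supplies Disclosure).** Use of the call center is limited to emergencies, with a reference to Section 8.1.11. The IRT system is the backup if the call center is not available to a site.
- **Section 8.1.3 (Participant Identification Card).** The card carries the call center's contact details "so that a healthcare provider can obtain information about study intervention in emergency situations where the investigator is not available".

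**The concern.** Appendix 2 places a discussion with the sponsor before a code break that is, by its own wording, already required. It does not say how long the investigator should try to reach the sponsor, what to do if nobody answers, or whether urgency waives the step.

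What is at stake is participant safety. An investigator who follows Appendix 2 literally could hold back a code break while trying to reach the sponsor, in a case where the code is essential for treatment. The difference also leaves sites with two sequences for the same event and no statement of which governs.

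**Working it through.** No arithmetic applies. The check is to set the texts side by side and compare the order of events.

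| Source | Steps before the code is released | When the sponsor learns of it |
|---|---|---|
| Section 8.1.11 | Reasonable attempt to chart the adverse event assessment; call to the call center | The call center reports the unblinding; the Sponsor Clinical Director is notified once it has occurred |
| Section 6.8 | Call center, or IRT if that is unavailable | Not stated; refers to 8.1.11 |
| Section 8.1.3 | A healthcare provider may use the call center if the investigator is unavailable | Not stated |
| Section 10.2 (Appendix 2) | Consultation and discussion with the sponsor, then start of the process | Before unblinding starts |

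1. **Order.** Prior sponsor contact appears in Appendix 2 only. In Section 8.1.11 the sponsor is informed after the fact, through the call center's report and the notice to the Sponsor Clinical Director.

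2. **Treatment of preliminary steps.** The one thing Section 8.1.11 asks for before the call is a chart entry, and it waives that entry if it would hold matters up: "If it is not possible to record this assessment in the chart prior to the unblinding, the unblinding should not be delayed". Appendix 2 adds a second preliminary step with no corresponding waiver. The waiver in 8.1.11 concerns charting only, so it does not cancel the Appendix 2 step. It does show that the main procedure does not want a needed code break held up by preliminaries.

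3. **Which cases are affected.** Appendix 2 limits code breaks to essential cases and then applies the consultation when unblinding is required. The need has therefore been established before the extra step begins. Section 8 leaves study-related medical decisions with a qualified physician investigator, and a mandatory prior discussion fits poorly with that.

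4. **What the consultation could add.** Under Section 6.3.3, sponsor personnel involved in administering treatment or in clinical evaluation are themselves blinded. The discussion is therefore not a route to the code; the call center or IRT is still needed afterwards.

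5. **Whether the texts can both be obeyed.** They can when the sponsor is reachable: consult, then call. The defect is thus an added, open-ended step, not a complete contradiction. The two part ways in practice when the sponsor cannot be reached at once.

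**The case against.** The strongest reply is that the working procedure is already right. Section 8.1.11 is the dedicated section, Section 6.8 points to it, and nothing points to a laboratory appendix for unblinding. Appendix 2 uses the word should, not must. Nothing in the documents makes the call center or IRT check for sponsor agreement, so the sponsor cannot block a code break.

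The clinical stakes are also limited. Every arm contains atorvastatin, and the cohort is known from the run-in dose and the tablet count. The investigator therefore faces only two possible assignments: ezetimibe 10 mg with atorvastatin 10 mg against atorvastatin 20 mg, or ezetimibe 10 mg with atorvastatin 20 mg against atorvastatin 40 mg. The stopping rules in Section 7.1 for transaminases, CK and interacting drugs work without the code, and safety laboratory results are not blinded to the investigator. Harm needs an essential code break, an investigator who follows Appendix 2 over 8.1.11, and a sponsor who is out of reach. How reachable the sponsor is cannot be judged from these documents.

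All of this stands as a limit on size. It makes a harmful delay unlikely for any one participant. It does not remove the instruction: should is still direction to sites, Appendix 2 has no cross-reference back to 8.1.11, and no rule of precedence is given. Saying that stopping the drug usually suffices leaves the remaining cases, which are the ones that need the code. The aim of discouraging needless unblinding is already served by the restrictions in both 8.1.11 and Appendix 2.

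**Conclusion.** The point holds. Appendix 2 adds a sponsor-consultation step before a required emergency unblinding that Sections 8.1.11, 6.8 and 8.1.3 do not contain, and it sets no limit or exception. The mismatch in the text is certain. A resulting delay is possible and depends on a site following Appendix 2 at a time when the sponsor is not immediately reachable; its length would be the time taken to reach the sponsor. Few participants are likely to be affected, since code breaks are restricted to cases of need, but the documents give no expected number. Efficacy estimates, type I error, power and sample size are untouched. The correction should be made because the issue concerns participant safety and is cheap to remove.

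**What to change.** Replace the last sentence on emergency unblinding in Section 10.2 with: *If emergency unblinding is required, follow Section 8.1.11; prior consultation with the Sponsor is not required, and the Sponsor Clinical Director is notified as soon as possible after unblinding.* Inform all sites of the change.

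The cost is a one-sentence protocol correction and a site notice, with no change to the analysis. The Code of Conduct in Section 10.1.1 requires ethics-committee approval before significant revisions are implemented, apart from urgent safety changes. Whether this edit counts as significant is arguable, and the sponsor should settle that when filing it. The sponsor gives up a chance to argue against an unnecessary code break beforehand, but the existing restrictions in 8.1.11 and Appendix 2 remain in force.
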